9.2 SAMPLE SIZE DETERMINATION

Our series of RCTs suggest that IBMT showed significant effects in relatively small sample size ¹⁻⁴⁴. For example, a recent RCT in healthy older adults showed significant effects on quality of life (N=25) and in resting state functional connectivity and structural changes in the ACC/mPFC-Striatum networks following IBMT (N=13) ⁴; In adults, we detected significant fMRI signal changes in the ACC/mPFC (Cohen's $d = .90$) after 10-session IBMT ^{9,11}. We used GPower 3.1 software to determine the smallest detectable effect for a treatment X time interaction term given various sample sizes and a power of 0.80, assuming varying correlations between repeated measures, which ranged from .30 -.60 on behavioral and .50 -.80 on fMRI measures in our prior studies ¹⁻⁴⁴. Considering these factors, our target N of 40 after attrition will allow us to detect small-medium-sized effects on continuous outcomes. The N of 40 will provide a reasonable sample to determine the effect size of IBMT without utilizing an unreasonable amount of resources in this pilot. Specifically, 40 subjects will give us adequate statistical power (80%) to detect a medium effect size [$f = 0.3$ for ANOVA and $h = 0.6$ for proportion difference] with alpha=0.05 for analysis proposed. This effect size is conservatively estimated based on our previous studies ^{5,8-12}. The Chi-square test would be less statistically powerful; however, as the nature of this project is exploratory, we are interested in determining the potential effect size of intervention and in developing our intervention protocol in older adults before testing it in a larger sample size.

Given the 1-year project with pre, post-intervention and follow-up and power considerations, the N of 40 we choose is also in line with our intervention cycles and capacities.

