9.4 STATISTICAL ANALYSIS PLAN

9.4.1 GENERAL APPROACH

Behavioral and brain data analysis will undergo separate analyzing streams to test intervention effects and underlying mechanisms at different time points. Given the scope of this 1-year pilot project, the logical first step at this early stage of research is to examine the potential intervention effects and mechanisms in small sample size, then move to the full scale RCTs for replication. To address our study Aims, repeated-measures ANOVA will be used. By utilizing all assessment points, this approach allows for well-powered tests to detect significant differences in changes across the experimental conditions, even when assuming smaller magnitude effect sizes. Effect size measures (from the repeated-measures ANOVA, Cohen's d highlighting mean differences between treatment and control groups across assessments) will also be calculated to describe the intervention's effect on study outcomes.

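### Section 9.2's 80% power for a medium f = 0.3 with 40 participants does not reproduce, and its effect labels hide a need for differences of about 0.8 to 1.1 SD on the behavioral and cognitive endpoints

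*Combined protocol and SAP*

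**What the plan says.** Section 9.2 reports using GPower 3.1 "to determine the smallest detectable effect for a treatment X time interaction term", with correlations between repeated measures of .30 to .60 for behavioral and .50 to .80 for fMRI measures. It draws two conclusions for N = 40:

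- that this number, described as what remains after attrition, "will allow us to detect small-medium-sized effects on continuous outcomes";
- that it "will give us adequate statistical power (80%) to detect a medium effect size", given as f = 0.3 for the ANOVA and h = 0.6 for a difference in proportions, "with alpha=0.05 for analysis proposed".

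It adds: "This effect size is conservatively estimated based on our previous studies". The only prior effect size it quotes is a Cohen's d of .90 for an fMRI signal change. Section 9.4.1 repeats the message, calling the tests well powered "even when assuming smaller magnitude effect sizes".

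Section 9.2 does not say which GPower definition of f was used or which correlation lies behind the 80%. It does not translate f into a difference between arms.

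**The concern.** An f for a time x group interaction is not on the same footing as the f of a simple two-group comparison. The interaction f spreads the difference between arms over six cells (two arms by three visits), so a small-looking f can stand for a large difference. A reader of 9.2 would take *medium* to mean roughly half an SD between arms, especially as 9.4.1 says that effects will be reported as Cohen's d.

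At stake is how the pilot is read. Someone who believes that small-to-medium effects were detectable could take a non-significant F as evidence against a moderate benefit, when the trial had a poor chance of showing one. The plan reports F and p values for each endpoint and intends to move on to full-scale trials, so the sensitivity of this one should be stated correctly.

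**Working it through.** **Inputs.** N = 40 and alpha 0.05 (9.2); two arms (4.1); three visits, time x group F test (9.4.2); rho .30 to .60 behavioral, .50 to .80 fMRI (9.2). Section 5.5 expects 36 of 40 to complete, and 9.3 analyses only those with all ten sessions and usable data, so N = 36 is also shown. Assumed: 1:1 allocation, sphericity, no allowance for the age and sex covariates. SD is the within-arm SD at one visit.

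**Step 1: the plan's own figure.** GPower's default interaction definition, as I understand it, has noncentrality lambda = f² × N × m / (1 − rho), with m = 3 and df = (m − 1) and (N − 2)(m − 1), here 2 and 76. For f = 0.3, lambda = 0.09 × 40 × 3 / (1 − rho) = 10.8 / (1 − rho).

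| Reading of f = 0.3, N = 40 | lambda | Power |
|---|---|---|
| Default interaction f, rho .30 / .50 / .60 | 15.4 / 21.6 / 27.0 | 94.1 / 98.8 / 99.7% |
| Default interaction f, rho 0 (not a documented value) | 10.8 | 83.0% |
| lambda = f² × N × (m − 1) | 7.2 | 65% |
| Two-group ANOVA at one visit (d = 0.6), df 1 and 38 | 3.6 | 46% (80% needs N = 90) |
| d = 0.6 at both follow-ups, planned F, rho .30 / .50 / .60 | 3.4 / 4.8 / 6.0 | 35 / 47 / 57% |

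No row using the documented correlations gives 80%. With N = 36, the default reading gives 91.4 to 99.4%.

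**Step 2: what the interaction f means in SD.** Suppose the arms differ by 0, D and D at the three visits. The mean difference is 2D/3, so the interaction effects are D/3, D/6 and D/6 in absolute value in each arm. Their mean square over six cells is 2 × (D²/9 + D²/36 + D²/36) / 6 = D²/18. Hence f = D/√18 = D/4.243, and f = 0.3 means D = 1.27 SD.

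**Step 3: the difference with 80% power.** Solve step 1 for f, then D = 4.243 × f.

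| rho | f, N = 40 | D, N = 40 | D, N = 36 |
|---|---|---|---|
| .30 | .242 | 1.03 SD | 1.08 SD |
| .50 | .204 | 0.87 SD | 0.92 SD |
| .60 | .183 | 0.78 SD | 0.82 SD |
| .80 | .129 | 0.55 SD | 0.58 SD |

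Simulation of the F test (20,000 runs, N = 40) gave 79.5% at D = 1.02, rho .30, and 79.6% at D = 0.77, rho .60.

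**Step 4: power for moderate differences, rho .30 to .60.**

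| D | N = 40 | N = 36 |
|---|---|---|
| 0.6 SD | 35 to 57% | 32 to 52% |
| 0.5 SD | 25 to 42% | 23 to 38% |

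**Step 5: the companion claim.** For h = 0.6 with 20 per arm, 0.6 × √(20/2) − 1.96 = −0.063, so power is about 47.5%. For 80%, n per arm = 2 × (1.96 + 0.84)² / 0.36, which is about 44.

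**Sensitivity, rho .30 to .60.** At alpha 0.05/4 = 0.0125, the strictest FDR step over the four primary endpoints, the 80% difference is 0.92 to 1.22 SD (N = 40) or 0.97 to 1.29 SD (N = 36). If the effect halves by follow-up, it is 0.90 to 1.18 SD (N = 40).

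**The case against.** The strongest reply is that 9.2 names the interaction as the powered term, so the default interaction scale is the natural reading. There, f = 0.3 has more than the 80% claimed, even with 36. The detectable f of .18 to .24 also lies between the customary small (.10) and medium (.25) values of f, so the *small-medium* sentence fits that scale. This stands. A reader might infer from the SD figures that the power claim simply fails; the documents do not support that, because on this scale the 80% is exceeded. What remains is that the stated 80% is not the result of the stated inputs, and that the label conceals the size of difference required.

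A reader might also infer that f = 0.3 was meant as d = 0.6. It would match h = 0.6, and *conservative* would make sense beside d = .90, whereas 1.27 SD exceeds that figure. But 9.2 never says so, nor whether the .90 is a between-arm or within-arm effect. The single-visit 46% is also not the planned test.

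The project is a pilot meant to estimate effect size, 9.4.1 plans to report effect sizes, and nothing says that a null result will be read as no benefit. That misreading is a risk, not a plan. Nor has it been shown that significant results would mostly be overestimates. Brain outcomes fare better: a sustained 0.9 SD has 83 to 99.7% power at rho .50 to .80 with N = 40, against 68 to 91% at the behavioral correlations. Section 9.2 also concedes that the chi-square test is weaker, but still places h = 0.6 under the same 80%.

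**Conclusion.** The point holds as a fault in the stated figure and its labels. With the documented correlations, 80% power for f = 0.3 at N = 40 does not reproduce under any reading tried: it is 94 to 99.7% on the default interaction scale, 65% with the alternative noncentrality, and 35 to 57% for the planned test if d = 0.6 was meant. Whichever reading applies, the planned test needs a sustained difference of 0.78 to 1.03 SD on behavioral and cognitive outcomes (0.82 to 1.08 SD with 36), and 0.55 to 0.87 SD (0.58 to 0.92 SD) on brain outcomes. By the usual d benchmarks (0.5 medium, 0.8 large; a convention, not from the plan), the first range is about large or above. The h = 0.6 claim is wrong outright, at about 47.5%.

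These figures rest on 1:1 allocation, sphericity, an effect held at both follow-ups, and alpha 0.05 before FDR. A fading effect or the FDR step raises the required differences. Severity is should-fix, because neither N nor the analysis changes.

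**What to change.** In 9.2, name the GPower effect-size option, the correlation and the number of visits, and replace the power sentences with:

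> With the 36 completers expected (40 in brackets), two-sided alpha 0.05 before FDR, three visits, 1:1 allocation, sphericity and an effect sustained at both follow-ups, the time x group test has 80% power for a between-arm difference of 0.82–1.08 SD (0.78–1.03) on behavioral and cognitive outcomes (rho .60–.30) and 0.58–0.92 SD (0.55–0.87) on brain outcomes (rho .80–.50). For behavioral outcomes, power is 32–52% (35–57%) for 0.6 SD and 23–38% (25–42%) for 0.5 SD. FDR over four endpoints raises these differences.

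Correct the h = 0.6 statement to about 47.5% power with 20 per arm, or remove it. Remove the unqualified *small-medium-sized* and *medium* labels in 9.2, and the clause "even when assuming smaller magnitude effect sizes" in 9.4.1.

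The cost is rewording two sections. No participants are added and no analysis changes, but the stated sensitivity becomes less favorable.

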4.4 END-OF-STUDY DEFINITION

A participant is considered to have completed the study if he or she has completed the baseline assessment, 10 intervention sessions, post-assessment, and 3-month follow-up assessment.

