5.5 STRATEGIES FOR RECRUITMENT AND RETENTION

We anticipate to enroll 40 participants (males and females) ages from 40 to 65 years old across different race and ethnicity based on local demographic characteristics. Subjects will be recruited through print and media ads within local community. This will include radio and online ads and recruitment through social media. Flyers will be distributed throughout the local community. Based on our and other's previous experiences in longitudinal studies, about 5-10% of participants will dropout over the study period due to illness or relocation. We plan a dropout rate of 10% for this brief intervention. We propose to recruit 40 older adults of which 36 (90%) will complete the study.

Compensation and Retention. Participants will be financially compensated with \$300 in total for completing the study protocol (approximately for 15 hours of time); participants who only partially complete the protocol will be compensated based on prorated hours. To maximize participant retention we will maintain contact with participants over time via frequent assessment intervals (e.g., requiring a functioning phone number and email address to contact participants by phone or email as needed, and obtaining the name, address, and phone number of at least 2 friends or classmates who can provide contact information for the participants, should we be unable to contact them during the study; emails and reminder phone calls prior to all study visits; offer flexible scheduling options for assessment (including weekends); provide fair compensation to participants; and maintain positive relations with participants. These procedures were used to maintain adequate participant retention in our prior NIH studies.

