7.2 PARTICIPANT DISCONTINUATION/WITHDRAWAL FROM THE STUDY

Participants are free to withdraw from participation in the study at any time upon request.

An investigator may discontinue a participant from the study for the following reasons:

- Significant study intervention non-compliance, unless varying compliance is an aspect of the study objectives
- Lost-to-follow up; unable to contact subject (see **Section 7.3, Lost to Follow-Up**)
- Any event or medical condition or situation occurs such that continued collection of follow-up study data would not be in the best interest of the participant or might require an additional treatment that would confound the interpretation of the study

- The participant meets an exclusion criterion (either newly developed or not previously recognized) that precludes further study participation

The reason for participant discontinuation or withdrawal from the study will be recorded. Subjects who sign the informed consent form and are randomized but do not receive the study intervention may be replaced. Subjects who sign the informed consent form, and are randomized and receive the study intervention, and subsequently withdraw, or are discontinued from the study, will not be replaced.

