9.3 POPULATIONS FOR ANALYSES

The analysis population will be Modified Intention-to-Treat Analysis Population. Specifically, these participants are those who completed the full-dose of the intervention (10 sessions) and have complete and usable data for the primary endpoints.

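### Section 9.2 claims 80% power for h = 0.6 with 40 subjects, but two arms give about 48% and no planned test compares proportions; it also counts 40 after attrition where Section 5.5 expects 36

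*Combined protocol and SAP*

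**What the plan says.** Section 9.2 (Sample Size Determination) states: "Specifically, 40 subjects will give us adequate statistical power (80%) to detect a medium effect size". It then gives f = 0.3 for ANOVA and h = 0.6 "for proportion difference] with alpha=0.05 for analysis proposed". The next sentence adds: "The Chi-square test would be less statistically powerful", and calls the project exploratory. Earlier in the same section, the sample is described this way: "our target N of 40 after attrition will allow us to detect small-medium-sized effects on continuous outcomes".

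Other sections bear on these statements:

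- Section 5.5: "We propose to recruit 40 older adults of which 36 (90%) will complete the study".
- Section 7.2: randomised subjects who never receive the intervention may be replaced, but those who receive it "and subsequently withdraw, or are discontinued from the study, will not be replaced".
- Section 4.4: a completer is someone who has "completed the baseline assessment, 10 intervention sessions, post-assessment, and 3-month follow-up assessment".
- Section 9.3: the analysis population is limited to those who took all 10 sessions and "have complete and usable data for the primary endpoints".
- Sections 9.4.2 and 9.4.3: every primary and secondary endpoint is tested by the time-by-group term of a repeated-measures ANOVA. The N-Back percentage correct enters as a score.
- Section 9.4.5: baseline characteristics are compared by t-tests.

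**The concern.** Section 9.2 attaches one power figure, 80%, to two different effect sizes. For two proportions with 20 subjects per arm, h = 0.6 is well below what the trial can detect with that power. The chi-square remark concedes lower power but gives no other figure, so the 80% stands as written. Because Section 9.4 contains no comparison of proportions, the claim is also attached to no test.

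The second problem is the sample size. Section 9.2 treats 40 as the number remaining after dropout; Section 5.5 treats 40 as the number recruited. Both cannot hold with the planned 10% dropout.

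What is at stake is the accuracy of the power statement. No planned test depends on h = 0.6. The ANOVA figure, however, is stated for 40 subjects when the plan expects 36 to complete.

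**Working it through.** **Inputs.** Two arms (Section 4.1). No allocation ratio is given; Section 4.1 says that total numbers are balanced, so 1:1 is assumed. Alpha 0.05, h = 0.6, f = 0.3 and N = 40 come from Section 9.2. Dropout of 10% and 36 completers come from Section 5.5. Sidedness is not stated. The null in Section 9.1 is one of no difference, so two-sided is the main case and one-sided is also shown.

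**Trying to reproduce 80% for h = 0.6.** For two independent proportions, power = Φ(h × √(n1 × n2/(n1 + n2)) − z), with z = 1.960 two-sided or 1.645 one-sided.

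| Subjects | h × √(n/2) | Two-sided | One-sided |
|---|---|---|---|
| 20 + 20 | 0.6 × √10 = 1.897 | Φ(−0.063) = 47.5% | Φ(0.252) = 60.0% |
| 18 + 18 | 0.6 × √9 = 1.800 | Φ(−0.160) = 43.6% | Φ(0.155) = 56.2% |

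The 80% does not reproduce. Unequal allocation cannot rescue it, because n1 × n2/(n1 + n2) is largest at 1:1 for a fixed total. Reading 40 as the number per arm gives 76.5% two-sided and 85.1% one-sided, but that is 80 subjects.

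Exact enumeration of the uncorrected chi-square test agrees. At 20 per arm, for h = 0.6, power is 47.8% with a control rate of 0.2 (against 0.478), 44.8% with 0.3 (against 0.594) and 47.4% with 0.5 (against 0.782).

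**What 80% would need.** Two-sided, n per arm = 2 × ((1.960 + 0.842)/0.6)² = 43.6, so 44 per arm or 88 in total. The smallest h detectable with 80% power is 2.802 × √(2/20) = 0.89 with 40 subjects and 2.802 × √(2/18) = 0.93 with 36.

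**Sample size.** 40 × 0.9 = 36, which matches Section 5.5. To keep 40 after 10% dropout, 40/0.9 = 44.4, so 45 would have to be recruited.

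**The ANOVA half, f = 0.3.** Section 9.2 names GPower 3.1 and the treatment-by-time interaction. It gives correlations of .30-.60 for behavioural measures and refers to pre, post and follow-up visits, so m = 3 is used here. It does not say which effect-size option was set. Alpha is 0.05 before any FDR correction, and sphericity is assumed.

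- Default option: λ = f² × N × m/(1 − ρ), with df m − 1 and (N − 2)(m − 1). At N = 36, λ = 0.09 × 36 × 3/(1 − ρ) = 13.9 (ρ = .3) or 24.3 (ρ = .6), with df 2 and 68. Power is 91.4% to 99.4%. At N = 40 it is 94.2% to 99.7%.
- 'As in SPSS' option: λ = f² × (N − 2)(m − 1). At N = 36, λ = 0.09 × 34 × 2 = 6.12 and power is 57.3%. At N = 40, λ = 0.09 × 38 × 2 = 6.84 and power is 62.6%.

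The same f therefore lies well above or well below 80%, depending on a setting that the section does not report.

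**The case against.** The best defence is that Section 9.2 itself warns that the chi-square test has less power, that the study is an exploratory pilot, and that nothing in Section 9.4 uses h = 0.6. All of that is true and limits the consequence. It does not make the 80% correct: the sentence assigns that power to both effect sizes, and the warning gives no replacement figure.

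A second defence is that sidedness and allocation are unstated and that the hypothesis in Section 9.1 is directional. This changes the size of the error, not its existence. The shortfall from 80% is about 32 points two-sided and 20 points one-sided with 40 subjects.

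A third defence concerns 36. A reader might infer that 36 is a ceiling on the analysed number. The documents do not establish that. Section 5.5 cites experience of 5-10% dropout, and 5% would leave 38 (40 × 0.95). Section 7.2 permits replacement before treatment starts. Also, the endpoint table in Section 3 names only baseline and post-intervention, so someone who misses only the 3-month visit might still count as having complete primary data. So 36 is the planned number of completers and no more than that. The conflict with 40 after attrition remains, because treated dropouts are not replaced.

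**Conclusion.** The point holds on two counts.

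1. The stated 80% power for h = 0.6 is wrong for this design: about 48% two-sided or 60% one-sided with 40 subjects, and about 44% or 56% with 36. These values assume 1:1 allocation; any other ratio gives less. The figure also corresponds to no planned analysis.
2. Sections 9.2 and 5.5 disagree on whether 40 is the number before or after attrition.

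Two stronger readings are tempting. A reader might infer that the primary ANOVA is underpowered. The documents do not show this: on the GPower default scale, f = 0.3 exceeds 80% with 36 subjects and three visits. A reader might equally infer that the ANOVA power is safe. That is not shown either, since the 'as in SPSS' option gives about 57%. The f = 0.3 claim is unverified, not refuted.

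Nor does Section 9.2 present f = 0.3 as a medium standardised difference between arms. It calls it a medium effect for ANOVA, so there is no such misstatement to correct.

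This should be fixed as a matter of accuracy and consistency.

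**What to change.** In Section 9.2:

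- Delete the h = 0.6 figure and the chi-square clause. If they are kept, restate the power as about 48% with 40 subjects and 44% with 36 (two-sided, 1:1).
- Replace the reference to 40 after attrition with 40 recruited and 36 expected to complete, in line with Section 5.5.
- Restate the f = 0.3 ANOVA power at N = 36 under the GPower effect-size option actually used, and name that option.

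The cost is rewording one section. Enrolment, endpoints and analyses do not change; the only downside is that the stated figures become less favourable.

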9.3 POPULATIONS FOR ANALYSES

The analysis population will be Modified Intention-to-Treat Analysis Population. Specifically, these participants are those who completed the full-dose of the intervention (10 sessions) and have complete and usable data for the primary endpoints.

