7.1 DISCONTINUATION OF STUDY INTERVENTION/EXPERIMENTAL MANIPULATION

If a clinically significant finding is identified (including, but not limited to changes from baseline) after enrollment, the investigator or qualified designee will determine if any change in participant management is needed. Any new clinically relevant finding will be reported as an adverse event (AE).

The data to be collected at the time of study intervention discontinuation will include the following:

- The reason(s) for discontinuing the participant from the intervention, and methods for determining the need to discontinue
- If the participant is due to complete assessments within 1 weeks of being discontinued from the study intervention, those assessments will be administered at the time of discontinuation; if the next scheduled assessments are more than 1 week from the discontinuation date, the next scheduled assessment will not be administered. Thereafter, the participant will be not included in all future scheduled assessments, as they did not participate in the intervention.

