9 STATISTICAL CONSIDERATIONS

9.1 STATISTICAL HYPOTHESES

- Primary Endpoint(s):

We hypothesize that, compared to participants who receive a control intervention, participants who receive IBMT for improving behavior and cognition will have improved working memory, emotion regulation, and reduced subjective report of cognitive decline after completing the intervention at post-assessment, and will continue to show improvement 3 months after the intervention. Alternatively, our null hypothesis is that there will be no difference in the effects of IBMT for improving behavior and cognition and those of control intervention at post-assessment or after 3 months of intervention.

- Secondary Endpoint(s):

We hypothesize that, compared to participants who receive a RT control intervention, participants who receive IBMT for improving brain function and structure will have improved white matter, grey matter, and functional connectivity in AD-signature regions after completing the intervention at post-assessment, and will continue to show improvement 3 months after the intervention. Alternatively, our null hypothesis is that there will be no difference in the effects of IBMT for improving brain function and structure and those of RT at post-assessment or after 3 months of intervention.

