9.4.2 ANALYSIS OF THE PRIMARY ENDPOINT(S)

The primary endpoints are behavioral and cognitive assessments and are all repeated measures assessed at baseline, post-intervention, and 3-month follow-up. For cognitive assessment of N-Back working memory, percentage of correct trials will be calculated for each trial for all endpoints. For behavioral assessment of emotion regulation, mindfulness, and SCD, these self-report questionnaires will be calculated based on established scoring guides by summing all items within a given questionnaire for all endpoints. Next, the effects of intervention (IBMT vs. HE) on each of these primary endpoints will be examined using repeated-measures ANOVA with time x group interaction effect. Variance and covariance across repeated measures will be calculated as part of the ANOVA. Age and sex will be included as covariates to control for potential confounding effects of age and sex on behavioral and cognitive assessments. Results will be presented as F values for the interaction effect, along with p values to indicate statistical significance. Normality and homogeneity of variance assumptions will be checked using SPSS built-in tools for ANOVA. Because there are 4 primary endpoints, multiple comparison corrections will be conducted using FDR correction. Missing data will be handled with case-wise deletion.

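### The only analysis population is called modified ITT but is a completers set, and no analysis of all randomised participants is planned

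*Combined protocol and SAP*

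**What the plan says.** Section 9.3 defines a single analysis population and calls it modified intention-to-treat. Its members are then limited: "these participants are those who completed the full-dose of the intervention (10 sessions) and have complete and usable data for the primary endpoints". Section 6.1.2 defines full dose as all 10 sessions. Section 4.1 places randomisation before the baseline assessment, so neither condition can be known when participants are allocated.

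Sections 9.4.2 and 9.4.3 handle missing data by case-wise deletion. Each primary endpoint "will be examined using repeated-measures ANOVA with time x group interaction effect", over baseline, post-intervention and 3 months. No section plans an analysis of everyone randomised, or a sensitivity analysis to the population. ITT on its own appears only in the abbreviation list (10.3).

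Section 7.1 governs data collection after a participant is discontinued from the intervention. An assessment due within 1 week is done at the time of stopping. Otherwise, "if the next scheduled assessments are more than 1 week from the discontinuation date, the next scheduled assessment will not be administered". The rule goes on: "Thereafter, the participant will be not included in all future scheduled assessments, as they did not participate in the intervention". Section 7.2 lets an investigator discontinue a participant for significant non-compliance.

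Section 5.5 expects that "about 5-10% of participants will dropout over the study period due to illness or relocation", plans for 10%, and expects 36 of 40 to complete.

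**The concern.** A modified ITT set normally stays close to the randomised groups. This one does not: it keeps only people who attended every session and supplied every primary measurement. Someone with 9 sessions and full outcome data is left out, and a post-assessment that 7.1 collects from a person who stops cannot be used.

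Randomisation protects a comparison of the groups as allocated. It does not protect a comparison of those who finished, because finishing may depend on how a participant is responding, and that dependence may differ between IBMT and health education. Section 9.2 wants an effect size before a larger trial, and 9.4.2 and 9.4.3 plan p values. A completers-only estimate carrying an ITT label could be read as something it is not when the larger trial is planned.

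**Working it through.** **1. The plan's own figure.** From 5.5: 40 x (1 - 0.10) = 36, so 4 people are lost. This reproduces. Section 4.1 says numbers are balanced but gives no ratio. Assuming 1:1, 20 are randomised and 18 analysed per arm.

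**2. Who is in the set.** In 1.3, Visit 12 is Day 13 ±2, Visit 13 is Day 90 ±2, and sessions run to about Day 12. The 1-week rule in 7.1 gives a cut-off of Day 13 - 7 = Day 6 (Day 4 to Day 8 with the window). Nobody who stops during the sessions is within a week of Day 90.

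| Participant | Outcomes collected | In the 9.3 set? |
|---|---|---|
| 10 sessions, all primary data | all three visits | yes |
| 9 sessions, not discontinued | all three visits | no |
| Stops on Day 10 | baseline, post | no |
| Stops before about Day 6 | baseline only | no |

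The second and third rows hold outcome data that no planned analysis uses.

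**3. Bias under no true effect.** Let q be the share excluded in an arm and r the correlation between the tendency to complete and change in outcome. With z_q the standard normal quantile of q and phi the normal density,

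bias (in SD of change) = r1 x phi(z_q1)/(1 - q1) - r2 x phi(z_q2)/(1 - q2).

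The documents give neither r nor q by arm. I assume r of 0.3 to 0.5 and take q from the range in 5.5.

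- q = 10% in both arms, selection in one arm only: phi(z)/(1 - q) = 0.1755/0.90 = 0.195. Bias = 0.3 x 0.195 = 0.058 to 0.5 x 0.195 = 0.097.
- q = 5% in both arms, selection in one arm only: 0.033 to 0.054.
- Same q and same r in both arms: 0.
- r = 0 in both arms: 0, even if completion rates differ.
- Same r, different rates (20% against 0%, which no section supports): 0.105 to 0.175.

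**4. Against the noise.** With 18 per arm, the SE of the change contrast is sqrt(2/18) = 0.333 SD of change. Noncentrality at 10% is 0.058/0.333 = 0.18 to 0.097/0.333 = 0.29. On 34 degrees of freedom, a two-sided 0.05 t test on change then has type I error 0.053 to 0.059. Simulating the three-visit time x group F test, without covariates or the FDR step, gives 0.052 to 0.059. If completion depends on a stable level rather than on change, the change contrast is unbiased and the F test stays at 0.049 to 0.051.

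**5. What a mixed model recovers.** I simulated the baseline-to-post contrast with 20 per arm, r of 0.3 to 0.5, visit correlations of .30 and .60 (the ends of the behavioural range in 9.2), and exclusion of 10% per arm or 20% against 0%. People who stop supply only a baseline to the model. Absolute bias in SD of change:

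| Completion depends on | Completers | Mixed model | All outcomes collected |
|---|---|---|---|
| change | 0.05-0.17 | 0.03-0.13 | 0.00 |
| observed baseline | 0.02-0.10 | 0.00 | 0.00 |
| stable trait | 0.00 | 0.02-0.06 | 0.00 |

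The model alone is not a full cure, and in the last row it does slightly worse than completers. Collecting outcomes from people who stop removes the bias in every row.

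**The case against.** The rule is stated openly, and a full-dose question may be intended: 9.1 frames the hypothesis as an effect "after completing the intervention at post-assessment". The study is a self-described exploratory pilot. Several features make differential completion less likely. The control is also a coach-led group programme of 10 sessions (6.1.1, 6.1.2). Participants are not told which arm is experimental (6.3). Missed visits are to be rescheduled within a week (7.3), although whether a group session can be made up is not stated. The dropout reasons named in 5.5 need not differ by arm. All of this stands. It lowers the likely size of the problem but does not exclude it, and none of it makes the label right or supplies an all-randomised analysis.

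Three stronger readings are tempting, and the documents do not support them.

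- A reader might infer from 7.1 that the randomised comparison would be lost for good. But 7.1 covers people discontinued from the intervention, not someone who merely misses a session. People who leave after the sessions end also already have a post-assessment. If the 4 expected dropouts were spread evenly over 90 days (an assumption; they could come early), about 4 x 12/90 = 0.5 would stop during the sessions and 4 x 5/90 = 0.2 before Day 6. Much of an all-available-data analysis could still be run later.
- A reader might infer that requiring every session will exclude far more than 10%. No attendance rate is given, and 4.4 counts the 10 sessions as part of completing the study, so the planned 10% may already include incomplete attendance.
- A reader might infer that the Cohen's d in 9.4.1, described as "highlighting mean differences between treatment and control groups across assessments", compares levels and so would also absorb selection on a stable level. Section 9.4.1 derives it from the repeated-measures ANOVA and speaks of differences in changes, so that reading is speculative.

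**Conclusion.** The point holds and should be fixed. The only analysis population is a per-protocol completers set under a modified ITT label, and no planned analysis keeps the randomised groups intact. That much follows from the text alone.

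The numerical consequence is conditional and may be zero. Bias needs completion to be related to change, and either that relation or the completion rate to differ by arm. At the planned 10% loss the illustrated bias is less than a third of the standard error and type I error barely moves. These figures rest on assumed correlations, 1:1 allocation and selection in one arm only; the direction cannot be determined. The reason to act is that the rule is wrong as written and cheap to change, not that a large distortion has been shown.

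**What to change.** - **9.3:** make the main population all randomised participants, analysed as allocated, regardless of sessions attended. Keep the ten-session, complete-data set as a sensitivity analysis labelled per-protocol; it still answers the full-dose question.
- **9.4.2 and 9.4.3:** replace case-wise deletion with a likelihood-based mixed model for repeated measures on all available data, with the same group, time, group x time, age and sex terms. Specify a small-sample degrees-of-freedom method, such as Kenward-Roger, and state the missing-at-random assumption.
- **7.1 and the non-compliance clause of 7.2:** reconcile these with the new population, so that stopping or missing sessions does not by itself end outcome collection where the participant is willing and able. Leave the other discontinuation grounds as they are.
- **Reporting:** give sessions attended and reasons for missing data by arm.

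**Cost.** Text edits to five sections, and at the planned dropout at most 4 x 2 = 8 extra Visit 12 and Visit 13 assessments. The documents show no budget for these, and people lost to illness or relocation may not be reachable. The estimate may be smaller than among completers. The new population and model are worth adopting even without the extra visits, because they use outcomes already collected from people with fewer than 10 sessions. Where someone who stops supplies only a baseline, the result still rests on missing-at-random and some bias can remain.
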